## Study Protocol and Statistical Analysis Plan

This study is a randomized controlled trial at Magee-Womens Hospital in which individuals with a hypertensive disorder of pregnancy are randomized to the neonatal sleep intervention (the SNOO responsive bassinet), or usual care of safe sleep education in the postpartum period.

*Inclusion and Exclusion Criteria.* Individuals meet inclusion criteria if they are  $\geq 18$  years old, have a singleton, full-term (37 weeks or greater weeks of gestation), live birth of a non-anomalous fetus, a diagnosis of gestational hypertension or preeclampsia by ACOG criteria, are enrolled in the Connected Care (formerly known as Vivify) institutional remote monitoring program, and are willing to undergo randomization and use the SNOO for their neonate. Individuals will be excluded if they are  $< 18$  years old, non-English speaking, having chronic hypertension, pre-gestational diabetes, cardiac disease, kidney disease, or liver disease, have an infant admitted to the NICU, intend to use the SNOO prior to study enrollment, are not willing to be randomized, or are not willing to use the SNOO. Individuals who meet criteria will be approached during their postpartum admission. If the participant agrees to enroll in the study, she will be consented and randomized at that time. Randomization will occur via permuted blocks with randomly varying block sizes by a web-based data entry system.

*Study Overview.* Those randomized to the intervention will be oriented to the use of the SNOO (see Figure 1) and instructed to have their neonate sleep in the SNOO as often as they can, with the understanding that some sleep does occur outside of bassinets. The SNOO is a commercially available device which is a responsive bassinet for neonates, and designed to respond to the infant's cries and automatically respond by emitting engineered white noise sounds and providing a rhythmic rocking motion. The infant is also swaddled to remain securely back-down. The SNOO automatically increases the sound and motion if the infant is still crying. However, if the infant does not settle within 3 minutes, the SNOO shuts off and alerts adults for additional assistance. Parents can also modify the SNOO settings to meet the baby's need for sound and/or motion.

Figure 1: SNOO responsive bassinet

Participants receiving the SNOO will be also asked to download and use the SNOO Smart Sleeper mobile application using either their own name and email address (if they are comfortable) or a study-provided ID and email address. This mobile application provides daily sleep reports while the SNOO is in use, alerts the parents that the infant requires additional attention if the infant does not settle after 3 minutes of crying, and allows the parents to customize the sound and/or motion level the infant receives.

Participants both groups will both receive:

- Standard of care safe sleep education during their postpartum admission, including a handout on safe sleeping from the UPMC Healthwise educational database
- Routine postpartum management of their hypertensive disorder of pregnancy, which at Magee-Womens Hospital, consists of enrollment in the Connected Care remote monitoring program.
- BP cuff and a scale with instructions on their use

For both groups, participants will be requested to record vital sign parameters into the Connected Care institutional remote monitoring program through 6 weeks postpartum. There is one main study visit at 6 weeks postpartum, and one brief study visit at 4 months postpartum which will be conducted through video calls. Participants will complete an infant sleep log and a maternal sleep log for the 7 days leading up each of the planned study video visits. At each video visit, participants will be asked to take their weight and blood pressure. At the first video visit, a questionnaire will be administered which includes:

- Pittsburgh Sleep Quality Index (PSQI): 19 questions of subjective sleep quality
- PROMIS Sleep Disturbance Questionnaire: 27 questions regarding sleep quality
- Epworth Sleepiness Scale (ESS): 8 questions to assess daytime sleepiness

- Edinburgh Postnatal Depression Scale (EPDS): 10 questions to identify individuals at risk for postpartum depression
- Generalized Anxiety Disorder 2-Item (GAD-2): 2 questions to screen for generalized anxiety disorder
- Perceived Stress Scale 4 (PSS-4): 4 questions to assess stress level
- Breslau 7-Item (Breslau-7): 7 questions to screen for post-traumatic stress disorder
- Survey questions to assess demographic information, reproductive history, current health status, BP medications, infant feeding method, and SNOO use

Participants will be compensated up to \$60 paid on a VINCENT card. They will receive \$50 after completing the 6 week postpartum research visit, and \$10 after completing the 4 month postpartum research study visit.

See a visual representation of the study design in Figure 2:

[figure not shown]

Figure 2: Study Design

**Outcomes.** The primary outcome is mean arterial pressure (MAP) at 6 weeks postpartum. Secondary outcomes include MAP at 1 week and 4 months postpartum; systolic and diastolic BP at 1 week, 6 weeks, and 4 months postpartum; antihypertensive medication use at 1 week, 6 weeks, and 4 months postpartum; Stage 1+ Hypertension or antihypertensive medication use at 1 week, 6 weeks, and 4 months postpartum; maternal weight and body mass index at 1 week, 6 weeks, and 4 months postpartum; subjective sleep quality at 6 weeks postpartum using the PSQI, PROMIS, ESS; objective sleep assessment using sleep log data at 6 weeks and 4 months postpartum; and mood assessment at 6 weeks postpartum using the EPDS, GAD-2, PSS-4, and Breslau-7.

**Sample Size Calculation.** In current remote monitoring patients without a history of chronic hypertension, the mean MAP at 6 weeks (among 1,007 individuals) was  $94 \pm 8$  mmHg. With 1:1 randomization, 2-sided t-test with independent means, a sample size of 100 individuals total (50 per arm) would give an 80% power to detect a 4.5 mm Hg decrease in MAP. Additionally, for our secondary outcomes of systolic and diastolic BP at 6 weeks postpartum, we would be powered to detect a 6 mm Hg decrease in systolic BP and a 5 mm Hg decrease in diastolic BP with an alpha of 0.05, which would be a clinically meaningful outcome.

**Statistical Analysis.** Statistical analysis was performed using the intention-to-treat principle, with all randomized participants included in the analysis. All statistical was performed using Stata (StataCorp LLC, version 17.0, College Station, Texas, USA). Two-sample two-sided t-tests and Mann-Whitney U tests were performed to assess the differences between two groups of continuous, normally-distributed and non-normally distributed variables, respectively. Pearson's chi-square or Fisher's exact tests were performed to assess the differences between two groups of categorical variables. An alpha level of 0.05 was set for all statistical analyses. Pre-specified subgroup analyses include breastfeeding status, postpartum SARS-CoV-2 status, and a per-protocol analysis.

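### Must the plan define the primary 6-week MAP as a per-person average of home readings, rather than leave the BP source open?

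*Combined protocol and SAP*

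**What the plan says.** Outcomes defines the endpoint in one sentence: "The primary outcome is mean arterial pressure (MAP) at 6 weeks postpartum". It adds no source, window, reading count or combining rule, and Statistical Analysis adds none.

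Study Overview describes two BP sources.

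- **Video visits:** "There is one main study visit at 6 weeks postpartum, and one brief study visit at 4 months postpartum". On measurement: "At each video visit, participants will be asked to take their weight and blood pressure". The number of readings per visit is not given.
- **Connected Care, both arms:** "participants will be requested to record vital sign parameters into the Connected Care institutional remote monitoring program through 6 weeks postpartum". BP is included by fair inference, since both arms receive a cuff. The frequency of entry is not given.

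The planning figures in Sample Size Calculation come from a remote-monitoring cohort: "In current remote monitoring patients without a history of chronic hypertension, the mean MAP at 6 weeks" was 94 ± 8 mmHg in 1,007 people. The text does not say whether the 8 describes single readings or per-person averages. Statistical Analysis calls for intention to treat, "with all randomized participants included in the analysis", with no rule for a missed 6-week visit.

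Figure 2 (study design) is not available in the text reviewed and could name the source.

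**The concern.** The ambiguity falls on the primary time point. One-week MAP is a secondary outcome ("Secondary outcomes include MAP at 1 week and 4 months postpartum") but no 1-week visit is described, so among the described sources it can come only from Connected Care. Four-month MAP can come only from the video visit, because Connected Care entry is requested only through 6 weeks. At 6 weeks both sources are available.

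Three things appear to be at stake.

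1. **Precision.** If the visit reading alone is used, other readings already requested from both arms go unused.
2. **Planning.** If the SD of 8 describes per-person averages and the trial uses one reading, power is below the stated 80%.
3. **Missing data and flexibility.** A participant who misses the visit has no primary value unless Connected Care supplies one, and an unnamed source could be chosen after the data are seen.

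**Working it through.** **Inputs from the documents (Sample Size Calculation, Statistical Analysis):** difference 4.5 mmHg; 8 read as the SD; 50 per arm; two-sided t-test; alpha 0.05.

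**Inputs assumed, because the documents give none:** within-person correlation r from 0.5 to 0.9; k = 2 to 7 readings per person; serial coefficient c from 0.6 to 0.8; missed visits 10% or 20%.

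**Step 1. The plan's own figure.** Normal approximation: n per arm = 2(1.96 + 0.842)² × 8² / 4.5² = 49.6, so 50, with power 80.3%. Noncentral t: 50.6 per arm needed; power at 50 per arm is 79.5%; detectable difference at 80% power is 4.53 mmHg. The stated figure reproduces.

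**Step 2. Averaging, if 8 is the SD of a single reading.** For exchangeable readings, SD of the mean = 8 × √(r + (1 − r)/k). With first-order serial correlation in the within-person part, SD of the mean = 8 × √(r + (1 − r) × mean of c^|i−j|), the mean taken over all k² pairs (i, j).

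| Case | SD of mean | Power |
|---|---|---|
| One reading | 8.00 | 79.5% |
| Serial, r = 0.9, c = 0.8, k = 2 | 8√0.99 = 7.96 | 79.9% |
| Serial, r = 0.9, c = 0.8, k = 7 | 7.85 | 81.0% |
| Exchangeable, r = 0.9, k = 2 | 8√0.95 = 7.80 | 81.5% |
| Exchangeable, r = 0.7, k = 3 | 8√0.80 = 7.16 | 87.6% |
| Serial, r = 0.5, c = 0.6, k = 7 | 6.75 | 91.0% |
| Exchangeable, r = 0.5, k = 7 | 8√0.571 = 6.05 | 95.8% |

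If only 20% of participants have seven readings and the rest have one, the average variance is 64 × (0.2 × f² + 0.8), where f is the square-root factor above. Power is then 79.8% (serial, r = 0.9, c = 0.8) to 83.0% (exchangeable, r = 0.5).

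**Step 3. If 8 is already the SD of a per-person mean and the trial uses one reading.** Single-reading SD = 8/f.

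- Exchangeable, r = 0.9, k = 2: 8.21, power 77.5%.
- Serial, r = 0.9, c = 0.8, k = 7: 8.15, power 78.1%.
- Exchangeable, r = 0.7, k = 3: 8.94, power 70.2%.
- Exchangeable, r = 0.5, k = 7: 10.58, power 55.8%.

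**Step 4. Missed visits with no other source.** At SD 8, 45 per arm gives 75.1% and 40 per arm gives 70.0%. This is ordinary attrition at assumed rates. Nothing in the documents shows that people who miss the visit go on entering readings, so how much Connected Care would recover is unknown.

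**Step 5. What the arithmetic settles.** The direction is certain where a person has more than one reading of similar variance, not perfectly correlated, with little BP trend in the window. The size is not: steps 2 and 3 run from a fraction of a point to 16 points up or 24 points down, and the assumed inputs alone decide where the trial falls. If Connected Care readings are already to be averaged, both steps are moot.

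**The case for a change.** The strongest case for acting is that a primary endpoint should have one definition. At 6 weeks the visit reading, the last Connected Care entry and a window mean could each be called MAP at 6 weeks, and the choice could follow the data. Writing a rule costs a sentence and a data export, with no new burden on participants. It would also settle what the SD of 8 describes.

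The factual part stands: on the visible text the source, window and combining rule are unstated, and a report of the trial will have to name them. The rest is weaker.

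- **No inferior method is specified.** Nothing says the visit reading alone is the primary MAP. The planning data point at least as much toward Connected Care, and either source gives a valid two-arm comparison.
- **The averaging rule is a trade-off.** The visit reading is scheduled and requested in the same way in both arms. Connected Care entry is part of routine hypertension management and only requested, so the number of readings may depend on BP level, or on arm in a trial that describes no blinding. Counts by arm and a visit-only sensitivity analysis would reveal such an imbalance but not remove it.
- **The rule leaves its own gap.** With a window such as the 7 days ending at 6 weeks, a visit held a few days late falls outside it, and the plan gives no visit window. Six-week MAP could also become a multi-reading mean while 4-month MAP stays a visit measurement.
- **The planning mismatch is conditional.** It needs the SD of 8 to be an averaged SD and the trial to use fewer readings. Even then the r = 0.9 cases keep about 78% power. The trial's eligibility is also narrower than the planning cohort's description, so its SD may differ from 8 for other reasons.
- **Timing limits the benefit.** Statistical Analysis is written in the past tense. If outcomes have been seen, an averaged MAP could serve only as a labelled sensitivity analysis.

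**Conclusion.** No change to the plan follows. The omission is real, but it is a gap in detail that analysts can fill sensibly from either described source, provided both arms are treated alike. A fixed-window mean is a reasonable option, not a demonstrated improvement. Its gain over 79.5% power runs from 0.4 points (79.9%) to 16.3 points (95.8%), is nil if readings are already averaged, and carries a risk of uneven reading counts that the visit reading avoids.

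The 100-participant sample size reproduces, and the documents do not show the 80% power to be wrong. The power ranges rest on assumed correlations, reading counts and missed-visit rates, and on reading the 8 as an SD. The statement that the source is unnamed covers the visible text only, since Figure 2 could name it.

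### Does comparing measured 6-week MAP, whatever the antihypertensive use, leave the primary result misleading without a medication-corrected analysis?

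*Combined protocol and SAP*

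**What the plan says.** Under Outcomes: "The primary outcome is mean arterial pressure (MAP) at 6 weeks postpartum". The Statistical Analysis paragraph applies intention-to-treat to everyone randomized and gives the test for continuous variables: "Two-sample two-sided t-tests and Mann-Whitney U tests were performed to assess the differences between two groups of continuous". No sentence says what happens to the MAP value of a participant on an antihypertensive. The analyses listed at the end of that paragraph (breastfeeding, SARS-CoV-2, per-protocol) do not concern treatment either.

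Treatment is nevertheless in view elsewhere:

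- Both arms receive "Routine postpartum management of their hypertensive disorder of pregnancy, which at Magee-Womens Hospital, consists of enrollment in the Connected Care remote monitoring program".
- The questionnaire at the 6-week visit includes "Survey questions to assess demographic information, reproductive history, current health status, BP medications, infant feeding method, and SNOO use".
- The secondary outcomes include antihypertensive use on its own, and "Stage 1+ Hypertension or antihypertensive medication use at 1 week, 6 weeks, and 4 months postpartum".
- Categorical outcomes are compared as follows: "Pearson's chi-square or Fisher's exact tests were performed to assess the differences between two groups of categorical variables".

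On size, the Sample Size Calculation says that "a sample size of 100 individuals total (50 per arm") "would give an 80% power to detect a 4.5 mm Hg decrease in MAP", using a mean of 94 and an SD of 8 mmHg from 1,007 remote-monitoring patients.

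**The concern.** Blood pressure is both the outcome and a likely reason for giving drugs that lower it. If the bassinet lowers pressure, fewer women in that arm may need treatment. Drugs then pull the control mean down, and part of the benefit leaves the MAP difference and appears as less medication. A small or null MAP difference could then be read as no effect on blood pressure.

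The two medication outcomes do not seem to close the gap. They are binary, so they show that treatment differs but not by how many mmHg this moves the primary estimate. With 50 per arm, a test of medication use would also often miss a difference large enough to matter. The data for a supportive analysis are already collected at the 6-week visit, so leaving it out looks like an oversight.

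**Working it through.** **Inputs from the documents.** SD 8 mmHg, difference 4.5 mmHg, 50 per arm, two-sided alpha 0.05, unadjusted two-sample comparison.

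**Inputs not in the documents (assumed).** Drug effect on MAP *e* = 5 or 10 mmHg; control-arm use 10 to 30%; treatment given when 6-week MAP plus noise (SD 5) exceeds a threshold.

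**1. The plan's own figure.** SE = 8 × √(2/50) = 1.6 mmHg. Power ≈ Φ(4.5/1.6 − 1.96) = Φ(0.85) = 80.3%; by noncentral t it is 79.5%. The stated 80% is reproduced.

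**2. Attenuation formula.** If control use exceeds SNOO-arm use by Δp, then

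measured difference = 4.5 − Δp × *e*.

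With Δp = 0 the loss is zero, whatever the drug effect. If Δp is negative (more treatment in the SNOO arm), the measured benefit is exaggerated instead.

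**3. Size when the control arm matches the plan.** Solve for the untreated mean and SD so that *measured* control MAP is 94 with SD 8, at control use of 10, 20 and 30%. This assumes that the 1,007 patients included treated women, which the documents do not say.

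- The measured difference is 3.3 to 4.2 mmHg, a loss of 0.3 to 1.2 mmHg, or 0.3/4.5 = 7% to 1.2/4.5 = 27%.
- By the formula, these ends correspond to Δp of about 0.3/5 = 6 points and 1.2/10 = 12 points.
- Power is 1 to 7 points lower than for untreated MAP in the same scenario.

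**4. A less well-matched grid.** With untreated control MAP set at 96 or 97, SD 8.5 or 9, and thresholds of 102 to 106, Δp is 8.5 to 13.8 points. The formula gives:

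| Drug effect | Δp = 0.085 | Δp = 0.138 |
|---|---|---|
| 5 mmHg | 4.5 − 0.43 = 4.1 | 4.5 − 0.69 = 3.8 |
| 10 mmHg | 4.5 − 0.85 = 3.7 | 4.5 − 1.38 = 3.1 |

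That is a loss of 9 to 31%. At drug effect 10, however, these scenarios leave a measured control SD of 6.5 to 7.5, below the plan's 8, so step 3 is the fairer guide.

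**5. Against the trial's precision.** The 95% CI half-width for the MAP difference is 1.984 × 1.6 = 3.2 mmHg. A shift of 0.3 to 1.2 mmHg is about 9 to 38% of that.

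**6. What the medication comparison can show.** At 15.6% vs 7.1%, exact power is 27.6% (chi-square) or 15.9% (Fisher), and the CI half-width is 1.96 × √(0.156×0.844/50 + 0.071×0.929/50) = 12.3 points. At 30.6% vs 16.8%, the figures are 37.2%, 29.2% and 16.4 points. A non-significant test would not establish equal treatment.

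**7. What a fixed addition would do.** If a constant *c* is added to treated women's MAP, the difference becomes 4.5 + Δp × (*c* − *e*). Over Δp = 0.085 to 0.138:

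| True *e* | *c* = 0 (the plan) | *c* = 5 | *c* = 10 |
|---|---|---|---|
| 5 | 4.1 to 3.8 | 4.5 | 4.9 to 5.2 |
| 10 | 3.7 to 3.1 | 4.1 to 3.8 | 4.5 |

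When the true drug effect is 5, the plan underestimates by 0.4 to 0.7 mmHg, and adding 10 overestimates by the same amount.

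**The case for a change.** The strongest case for a change is that the remedy costs almost nothing: one sentence naming the question, and one extra comparison on data already in hand, shown over a range so that no single drug effect is trusted. Without it, a reader has no mmHg figure for how far treatment matters, and step 6 shows that a significance test on medication use cannot be relied on to raise the alarm. More severe inputs also give worse figures. A 20-point excess in control with a 10 mmHg drug effect leaves 4.5 − 2.0 = 2.5 mmHg, with 35% power at SD 8.

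Part of this stands. No planned analysis answers the question in mmHg, and the medication comparison should be read by its estimate and interval, not its p-value.

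The rest is weaker. The 35% figure needs an excess larger than any that the treatment models above produce, and it ignores that treating the highest values also narrows the spread. Those models assign treatment from 6-week MAP after the full bassinet effect has acted. Randomization takes place during the postpartum admission, and medication is already an outcome at 1 week. The documents do not say when treatment starts, and treatment begun before the bassinet could act would be balanced in expectation. Nor does the plan say that its 4.5 mmHg is an untreated effect. It is set against the SD of 6-week MAP seen in remote-monitoring patients, so no shortfall in the stated power has been shown.

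**Conclusion.** No change follows. Carried out as written, the plan gives a sound treatment-policy estimate: the difference in 6-week MAP under each assignment, with routine hypertension care as it occurs. The intention-to-treat statement and the unadjusted test leave an analyst little room to read it otherwise, so the missing estimand sentence is a gap that would be filled sensibly. A benefit that takes the form of less treatment is also not lost. It belongs to two listed secondary outcomes at the same visit, one of which counts treated women as events, and both will stand beside the MAP result.

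The possible attenuation is about 0.3 to 1.2 mmHg on a true untreated difference of 4.5, with 1 to 7 points of power. This holds only under assumed drug effects of 5 to 10 mmHg, control use of 10 to 30%, treatment driven by 6-week MAP, and a reference population that includes treated women. It is zero if use is balanced, and it reverses if the SNOO arm is treated more. An added-constant analysis would leave the primary result as it is and would reduce bias only if the constant were close to a drug effect that the documents do not give. It is a reasonable optional display, not something the plan lacks.

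### Weight and BMI at three follow-up times are compared without adjusting for a pre-randomisation weight: the comparison is valid but needlessly imprecise

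*Combined protocol and SAP*

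**What the plan says.** All references are to the combined protocol and SAP.

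- **Outcomes** lists "maternal weight and body mass index at 1 week, 6 weeks, and 4 months postpartum" as secondary outcomes. It names no reference weight, whether from before pregnancy, delivery or enrolment.
- **Statistical Analysis** gives one method for continuous outcomes: "Two-sample two-sided t-tests and Mann-Whitney U tests were performed to assess the differences between two groups of continuous, normally-distributed and non-normally distributed variables". No covariate adjustment is mentioned. It adds that "An alpha level of 0.05 was set for all statistical analyses".
- **Inclusion and Exclusion Criteria** puts recruitment in the hospital stay after birth: "Individuals who meet criteria will be approached during their postpartum admission". Consent and randomisation follow at that time, so all three weight time points come after randomisation.
- **Study Overview** gives both arms a "BP cuff and a scale with instructions on their use" and asks for weight at the two video visits. The text describes no weight taken before randomisation.
- **Sample Size Calculation** covers MAP, systolic and diastolic pressure. It makes no power claim for weight or BMI.

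**The concern.** Adults differ widely in weight for reasons that long predate delivery, and one woman's weights a few weeks apart can be expected to correlate strongly. A postpartum sleep intervention can act only on the course of weight after delivery. When follow-up weight is compared between arms with no baseline term, all of the pre-existing spread counts as noise. BMI brings no relief: it divides weight by a fixed height squared and keeps the person-to-person variation.

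What is at stake is precision. The intervals for weight and BMI would be wide enough to be compatible with both no effect and a sizeable one, when a single extra data item could narrow them considerably.

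**Working it through.** **Inputs from the plan:** 50 per arm, 1:1 allocation, two-sided alpha 0.05, 80% power; MAP SD 8 mmHg and target difference 4.5 mmHg.

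**Assumed inputs, not in the documents:** SD of maternal weight 12 to 20 kg; correlation r between pre-randomisation and follow-up weight 0.80 to 0.98; equal SDs at both times; no losses to follow-up.

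**Step 1. Reproduce the plan's own figure.** n per arm = 2(1.960 + 0.842)² × 8² / 4.5² = 49.6, which rounds up to 50. Power at 50 per arm is 80.3% by the normal approximation and 79.5% by the noncentral t. The plan's statement "a sample size of 100 individuals total (50 per arm) would give an 80% power to detect a 4.5 mm Hg decrease in MAP" reproduces.

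**Step 2. Detectable difference without adjustment.** The normal approximation gives (1.960 + 0.842) × √(2/50) = 0.560 SD. The noncentral t with 98 degrees of freedom gives 0.566 SD, which is used below.

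**Step 3. Effect of adjustment.** With baseline weight as covariate, the residual SD is SD × √(1 − r²). The detectable difference shrinks by the same factor (the one degree of freedom lost is ignored):

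- r = 0.80: √(1 − 0.64) = 0.60
- r = 0.90: √(1 − 0.81) = 0.44
- r = 0.95: √(1 − 0.9025) = 0.31
- r = 0.98: √(1 − 0.9604) = 0.20

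Detectable difference in kg at 80% power:

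| Assumed SD | Unadjusted | r = 0.80 | r = 0.90 | r = 0.95 | r = 0.98 |
|---|---|---|---|---|---|
| 12 kg | 6.8 | 4.1 | 3.0 | 2.1 | 1.4 |
| 15 kg | 8.5 | 5.1 | 3.7 | 2.7 | 1.7 |
| 18 kg | 10.2 | 6.1 | 4.4 | 3.2 | 2.0 |
| 20 kg | 11.3 | 6.8 | 4.9 | 3.5 | 2.3 |

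For BMI with an assumed SD of 5 to 8 kg/m², the unadjusted figure is 2.8 to 4.5 kg/m². At r = 0.95 it falls to 0.9 to 1.4 kg/m².

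**Step 4. Power for an illustrative 3 kg difference.** The documents name no target for weight, so 3 kg is only an example. Unadjusted power is 24%, 17%, 13% or 12% at SD 12, 15, 18 or 20 kg. With adjustment at r = 0.80, 0.90, 0.95 and 0.98 it is 54%, 81%, 98% and over 99% at SD 12 kg, and 24%, 40%, 66% and 96% at SD 20 kg.

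**Step 5. Is a change score needed?** Let Y be follow-up weight, W baseline weight and T the arm. If Y = a + τT + bW + error, then Y − W = a + τT + (b − 1)W + error. The treatment effect τ, its standard error and its p-value are identical. An unadjusted change score has SD × √(2(1 − r)), which beats the raw comparison only when r exceeds 0.5 and is never better than adjustment. At SD 18 kg it gives 6.4 kg against 6.1 kg at r = 0.80, and 4.6 kg against 4.4 kg at r = 0.90.

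**The case against.** **Stronger readings that a reader might infer.** The documents support none of these.

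- *The outcomes are wrongly defined and must become change scores.* Step 5 shows that once baseline weight is a covariate, level and change give the same answer. The gap is in the analysis method.
- *The raw comparison hides any effect, or is bound to be inconclusive.* It is valid. A true difference above about 0.57 SD would be detected with more than 80% power, and smaller ones with lower power.
- *A chance imbalance in starting weight would pass as an effect.* The t-test's standard error already allows for chance imbalance, and type I error stays at 5%. At SD 18 kg the standard error is 18 × √(2/50) = 3.6 kg, so significance needs an observed gap of about 1.98 × 3.6 = 7.1 kg. A gap of a few kilograms would not reach it.

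**The case for leaving the plan alone.** Weight and BMI are one entry in a long secondary list with no power claim. The six comparisons are nearly three, because BMI largely repeats weight. The SD, r and 3 kg are all assumed. A delivery-admission weight includes the pregnancy and comes from a different scale, so r may be well below 0.95. The analysis paragraph is in the past tense, so an enrolment weight may no longer be obtainable. The study design figure is not shown, so collection of a baseline weight cannot be ruled out.

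**What stands.** These points limit the importance and the size of the gain, and they are why r = 0.80 is in the table. They do not reverse its direction: adjustment helps at any appreciable correlation, and r = 0.80 still removes 40% of the detectable difference. Even if a baseline weight was collected, the stated tests do not use it. A charted admission weight can be sought after the event.

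**Conclusion.** The point holds as a minor one about precision in secondary outcomes. As written, the weight comparisons can detect about 0.566 SD, or 6.8 to 11.3 kg for an assumed SD of 12 to 20 kg. Adjusting for a pre-randomisation weight would bring this to between 60% and 20% of that for r from 0.80 to 0.98. The percentages depend only on r; the kilogram figures depend on the assumed SD as well. The loss is of precision, not validity, and nothing here affects the primary MAP conclusion.

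**What to change.** Keep the outcomes as listed. In Statistical Analysis, state that weight and BMI at each follow-up time are compared between arms by linear regression (ANCOVA), with the corresponding weight or BMI dated before randomisation as covariate. Take that weight from the delivery-admission record, or measure it at enrolment before randomisation. Name the source in the plan and use the same one in both arms. Change from that weight may be reported descriptively. State that the 1-week value is not to be used as baseline, because it follows randomisation and may already reflect the allocated arm.

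If the unadjusted results have already been seen, report the adjusted analysis beside them and label it as added afterwards.

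The cost is one extra data item per participant, with no added patients or visits. The downside of a charted pre-delivery weight is that it includes the pregnancy and comes from a different scale than the home weights. That lowers the correlation, and so the gain, but does not bias the comparison. An enrolment weight taken after delivery and before randomisation avoids the pregnancy component where it is still possible to collect one.

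### The sleep logs are listed as an objective assessment, but they are open-label participant reports and cannot support an objective sleep claim

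*Combined protocol and SAP*

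**What the plan says.** The Outcomes paragraph of the combined protocol and SAP names two kinds of sleep outcome, one after the other. The first is "subjective sleep quality at 6 weeks postpartum using the PSQI, PROMIS, ESS". The second is "objective sleep assessment using sleep log data at 6 weeks and 4 months postpartum".

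The Study Overview says where the log data come from: "Participants will complete an infant sleep log and a maternal sleep log for the 7 days leading up each of the planned study video visits". The questionnaires are given at the first video visit only, at 6 weeks.

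The opening paragraph says that individuals "are randomized to the neonatal sleep intervention (the SNOO responsive bassinet), or usual care of safe sleep education in the postpartum period". Nothing in the document describes masking, a sham device or a blinded assessor.

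The Study Overview also says: "Participants receiving the SNOO will be also asked to download and use the SNOO Smart Sleeper mobile application". It describes the app's output as follows: "This mobile application provides daily sleep reports while the SNOO is in use". No app is mentioned for the usual-care arm, and app data are not listed as an outcome. The instruction to use the bassinet is given "with the understanding that some sleep does occur outside of bassinets".

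**The concern.** The plan places *objective* directly against *subjective*, so a reader will take the word as a statement about the kind of evidence. A diary kept by a parent who knows the allocation is not objective in the usual sense. The maternal log is self-report. The infant log is a parent's report on the infant.

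The label affects what the trial can say about sleep. The intervention is described as a sleep intervention and the primary outcome is blood pressure. The document states no mechanism and plans no mediation analysis, but improved sleep is the natural link a reader would draw. If the logs were reported as objective and agreed with the questionnaires, the agreement would look like confirmation from an independent source. In fact both would carry the same open-label reporting bias. Eligibility requires willingness to use the device, so expectations about it are plausible in both arms.

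**Working it through.** **1. Set the sleep measures side by side.**

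| Measure | Who supplies the data | Knows the arm? | When | Plan's label |
|---|---|---|---|---|
| PSQI, PROMIS, ESS | Participant | Yes (inferred) | 6 weeks | Subjective |
| Maternal sleep log | Participant | Yes (inferred) | 6 weeks, 4 months | Objective |
| Infant sleep log | Participant, about the infant | Yes (inferred) | 6 weeks, 4 months | Objective |
| App sleep reports | Device, SNOO arm only, while in use | – | Daily | Not an outcome |

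Knowledge of arm is an inference: a bassinet in the home cannot be hidden, and no masking is described. On the two features that matter for objectivity, who reports and whether they know the arm, the logs and the questionnaires are the same. They differ in being kept over 7 days rather than answered once. That may reduce recall error, but it does not remove reporting by an unblinded participant.

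**2. Look for an instrumented measure that could justify the label.** None is listed as an outcome. The app is the only device-based source of sleep data. It is absent in the control arm and covers only time in the SNOO, while the plan accepts that some sleep happens elsewhere. It could not serve as an objective comparison between arms.

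**3. Count what rests on the logs at each visit.** At 6 weeks there are three questionnaires and two logs. At 4 months there are two logs and nothing else on sleep.

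**4. Trace how far the app could affect the logs.** Two logs at two visits make four log-visit combinations. The app reports could inform the infant log in the SNOO arm, which is two of the four, and then only for sleep in the device. Nothing suggests that they reach the maternal log.

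**5. Check the plan's own figure.** The Sample Size Calculation covers MAP, not sleep. With a difference of 4.5 mmHg, an SD of 8 and two-sided alpha 0.05:

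n per arm = 2 × (1.96 + 0.8416)² × 8² / 4.5² = 2 × 7.849 × 64 / 20.25 = 49.6, so 50.

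Power at 50 per arm is 80.3% by the normal approximation and 79.5% by the noncentral t. The stated figure reproduces. No log data enter it.

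**6. Illustration only.** The documents give no log variable, SD or reporting bias. Suppose there is no true effect, 50 complete logs per arm, and a reporting difference between arms of b SD. The t-test then has 98 degrees of freedom and noncentrality b × √(50/2) = 5b.

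| Assumed b (SD) | Noncentrality 5b | Chance of p<0.05 |
|---|---|---|
| 0 | 0 | 5.0% |
| 0.1 | 0.5 | 7.9% |
| 0.2 | 1.0 | 16.8% |
| 0.3 | 1.5 | 31.8% |
| 0.5 | 2.5 | 69.7% |

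The same table would apply to any unblinded self-reported outcome in this trial, including the questionnaires. Renaming the logs changes none of these values. The table shows why open-label self-report needs cautious reading. It does not measure the harm done by the word *objective*.

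**The case against.** The strongest reply is that *objective* is used loosely here. The first item concerns perceived sleep quality, and the logs may record quantities such as hours slept. A diary kept over 7 days is also a respectable instrument. Both remarks are fair and show that the logs are worth analysing. Neither makes the label right: the text does not say that it means logged quantities, and a reader will not assume so.

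A second reply is that this is one of many secondary outcomes and that no document promises to use the logs to confirm the questionnaires. That is true, and it limits the weight of the point.

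A reader might go further and infer that the SNOO arm copies its logs from the app while controls rely on memory, so that measurement differs by arm as a matter of fact. The documents do not support that. They do not include the log form or its instructions, do not say what source either arm uses, and do not say that any log is filled in by recall. App use is a possible route of bias for part of the infant log only.

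A reader might also take the rejection rates in the illustration as the size of the defect. They are ordinary t-test power at assumed biases, with complete logs assumed from everyone.

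**Conclusion.** The label is wrong as written. The logs are participant-reported and open-label, no instrumented sleep outcome is listed, and the plan therefore claims a property that the design lacks. The conclusion rests on the text and on one inference, that participants know their arm. It does not depend on the app or on any assumed bias.

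The scope is one secondary outcome at two visits. It matters most at 4 months, where the logs are the whole of the listed sleep evidence. Unequal access to app reports is a possible additional bias in the infant log and should be disclosed as such. Its size, and that of any other reporting bias, cannot be obtained from the documents.

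The logs remain usable as a diary. The MAP outcome and its sample size are not affected.

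**What to change.** In Outcomes, replace "objective sleep assessment using sleep log data at 6 weeks and 4 months postpartum" with *participant-reported sleep diary (infant and maternal logs), 6 weeks and 4 months*. Group it with the PSQI, PROMIS and ESS as self-reported sleep, and make no objective-sleep claim from it. When results are reported, present log differences as open-label self-report, and do not treat agreement with the questionnaires as independent confirmation.

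State that app sleep reports were available in the SNOO arm only, and do not use app data for any comparison between arms.

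If logs are still being collected, add one item recording whether app data were used to complete the infant log. The Statistical Analysis paragraph is written in the past tense, so collection may be over. In that case the item comes too late, but the relabelling and the disclosure can still be made.

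The cost is a few words in the outcome list, one sentence of disclosure and, where feasible, one item on the form. The downside is a weaker sleep claim. No visit, device or sample-size change is needed.
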